10.9. Index Procedure

For the Randomized Studies, subjects must undergo the procedure for which they were randomized to. Subjects treated with a modality they were not randomized to will be considered a major protocol deviation. CEAP 6 subjects in the VLU Study will not be randomized and will all be treated with the VenaSeal™ system.

The index procedure should be performed according to the current and applicable version of the manufacturer's IFU (if applicable) to the region of the study site. AE reporting for all subjects (Randomized Studies and VLU Study) will begin from the moment the index procedure is initiated, in line with the reporting requirements described in section 12: Adverse Events and Device Deficiencies of the protocol.

All Subjects:

The primary target vein must be treated first during the index procedure, and the remaining target veins will be treated in succession.

Procedure for VenaSeal™ closure system (CEAP 2-5 subjects in Randomized Studies assigned to VenaSeal™, or CEAP 6 subjects in VLU Study):

Prophylactic medications for potential allergic reaction to VenaSeal™ adhesive may be administered to the subject per the treating physician's discretion. Compression therapy and wound care dressings (VLU subjects) will be removed prior to the start of the procedure, if applicable.

Local anesthetic including tumescent and light sedation (including but not limited to oral Xanax and Valium) may be utilized. All other types of anesthesia including general, regional, and heavy sedation are not permitted for the VenaSeal™-treated subjects.

The IFU for the VenaSeal™ system applicable per region should be referred to for the procedure.

Procedure for surgical stripping (CEAP 2-5 subjects in Randomized Studies assigned to surgical stripping):

All types of anesthesia including general, heavy and light sedation, regional or local anesthesia may be used, per site's standard practice. Compression therapy will be removed prior to the start of the procedure, if applicable.

Surgical stripping was performed per physician's or site's standard practice. Enrollment was closed as of 22-Feb-2022 in the VenaSeal vs. Surgical Stripping Study.

Procedure for ETA (CEAP 2-5 subjects in Randomized Studies assigned to ETA):

Local anesthetics including tumescent and light sedation (including but not limited to oral Xanax and Valium) may be utilized. All other types of anesthesia including general, regional, and heavy sedation are not permitted for the ETA-treated subjects. Compression therapy use will be removed prior to the start of the procedure, if applicable.

The subject can be treated with either RFA or EVLA per site's standard practice and treating physician's discretion. Also, any RFA or EVLA device approved in the site's region can be used per site's standard practice. The manufacturer's current IFU applicable per region should be referred to for the procedure.

Adjunctive Therapies & Treatments

If the target limb is CEAP 4b, or 5, incompetent perforating veins may be treated per the investigator's standard of care using approved devices or procedures during the index procedure. If any other devices are used during the index procedure to treat the incompetent perforating veins, then data will be collected on other devices as applicable. The devices used for the incompetent perforating veins procedure should have regulatory approval applicable per region. If the incompetent perforating veins are treated post index procedure (permitted 3 months after index procedure) for CEAP 4b or 5 target limb, then data will be collected from 3 months through study end.

VLU Study: For CEAP 6 subjects, incompetent perforating veins may be treated per the investigator's standard of care using approved devices or procedures during the index procedure or at any time after the index procedure. If any other devices are used during or after the index procedure to treat the incompetent perforating veins, then data will be collected on other devices as applicable throughout the study. The devices used for the incompetent perforating veins procedure should have regulatory approval applicable per region.

VLU Study: Foam sclerotherapy may be injected into the ulcer bed, per site's standard of care. Subjects with VLUs will continue with ongoing wound care therapy, or have it initiated, as directed by a wound care physician until wound healing has been verified by the core laboratory.

For subjects undergoing surgical stripping, adjunctive procedures such as phlebectomy of tributaries can be performed during the index procedure, per the treating physician's discretion. For ETA or VenaSeal™ subjects, any adjunctive treatment of varicosities in the target limb such as phlebectomy or sclerotherapy cannot be performed along with the index procedure.

Subjects for all studies may return to the site after 3 months (calculated as 90 days) following the index procedure to complete additional adjunctive therapies of target limb varicosities per the treating physician's discretion; these treatments will be considered routine care. The data for the adjunctive therapy treatment will be collected through 60 months.

Other truncal veins in the non-target limb may not be treated at the time of the index procedure or within 30 days prior to or 3 months post-index procedure.

Post-Procedure

At the completion of the procedure, when treatment of all target veins has been completed, vessel occlusion (VenaSeal™ or ETA) or absence of refluxing target vein or residual target vein (surgical stripping) will be confirmed by DUS. Subjects should be provided pain, allergy and/or anti-coagulant medication at the treating physician's discretion as appropriate for the treatment received. Upon discharge, subjects should follow the site's standard post-operative instructions.

At the index procedure visit, the following procedural data shall be recorded for each subject in the study:

1. Date of procedure.
2. Code for physician conducting the procedure, as indicated in a coded log provided to sites.
3. VenaSeal-randomized and CEAP 6 subjects: Number of VenaSeal™ system procedures the treating physician has completed to date.
4. VenaSeal-randomized and CEAP 6 subjects: Identification data of the VenaSeal™ kits utilized for treatment.
5. Procedure times as described in the CRF specifications.
6. Medications: anesthetic, prophylactic, and post-procedural medications.
7. Pre-procedure length measurement of clinically relevant superficial truncal disease in target veins with a tape measure applied outside of the target limb prior to sterile field.
8. Chosen vein access sites for each target vein as well as type of access utilized.
9. Distance of vein access from the tibial tuberosity, if below the knee.

Medtronic Business Restricted

CONFIDENTIAL

056-F275, v B Clinical Investigation Plan Template

10. VenaSeal-treated subjects: points of aneurysm, tributaries, or perforators per target vein when multiple VenaSeal™ aliquots are utilized.
11. Post-procedure DUS: assessment of patency, stump length, reflux along treatment area, evidence of thrombus.
12. Post-procedure measurement of actual treatment length using a tape measure to measure the difference between the clinically relevant lowest point of reflux to the access point.
13. Physician satisfaction with the procedure.
14. AE assessment from the moment the index procedure was initiated.
15. VenaSeal™ system treated subjects: Device deficiencies related to the VenaSeal™ system.
16. Treatment issues experienced by the treating physician.
17. Subject's use of compression stockings upon discharge.

10.10. Follow-Up Visits: All Subjects

The VenaSeal vs Surgical Stripping Study patients will stop any follow-up assessments after the 12-month visit.

Day 7 (+/- 2 days)

Patients will return to the site for follow-up for the following assessments (limb-specific assessments are of the target limb only):

1. DUS:
 - a. Areas of patency, if any
 - b. Reflux along treatment area
 - c. Evidence of thrombus
2. rVCSS
3. Patient reported outcomes:
 - a. Pain score measured by using NRS scale of 0-10
 - b. Patient-reported symptoms
 - c. Ability to return to work/normal activities
 - d. VenousDQoL
4. AE assessment
5. Healthcare utilization since last study visit
6. VLU Study:
 - a. Active ulcers: ulcer assessment, ongoing wound care, photographs for core laboratory, healing status
 - b. Post-healing confirmation: recurrence status.

Day 30 (+/-7 days)

1. DUS:
 - a. Areas of patency, if any
 - b. Reflux along treatment area.
 - c. Evidence of thrombus
2. rVCSS
3. Peri-procedural Venous Treatment Satisfaction Questionnaire (VenousTSQe) and Venous Treatment Satisfaction Questionnaire (VenousTSQs)
4. EQ-5D-5L
5. AVVQ
6. SF-36
7. Patient reported outcomes:
 - a. Pain score measured by using NRS scale of 0-10
 - b. Ability to return to work/normal activities (only if not returned to work/normal activities by 7-day visit)
 - c. VenousDQoL
 - d. Patient-reported symptoms
8. AE assessment
9. Healthcare utilization since last study visit
10. VLU Study:
 - a. Active ulcers: ulcer assessment, ongoing wound care, photographs for core laboratory, healing status
 - b. Post-healing confirmation: recurrence status.

If COVID-19 prevents patients from returning for follow-up visits at 7 or 30 days (due to subject contracting COVID-19 or due to site policy), these visits may be conducted through telehealth or other alternative methods to be discussed with the Medtronic study team prior to execution.

3+ Months (calculated as 90 days): Optional for all subjects

1. Adjunctive therapy: Number of phlebectomy sites and/or sclerotherapy injections administered (data collected through 60 months).
2. AE Assessment.

6 months (+/- 4 weeks), 12, 24, 36(+/-8 weeks)

Subjects will return to the site for follow-up to conduct the following assessments (limb-specific assessments are of the target limb only). VenaSeal vs Surgical Stripping Study subjects will be followed up to and including 12 months:

1. DUS:
 - a. Areas of patency, if any
 - b. Reflux along treatment area
 - c. Evidence of thrombus
2. CEAP classification
3. rVCSS
4. Venous Treatment Satisfaction Questionnaire (VenousTSQs) (up to 12 months visit)

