10.1. Schedule of Events and Data Collection

An overview of all data collection requirements is given in **Table 6** and **Table 7** below. All subjects (in the Randomized Studies as well as the VLU Study) will follow the assessment schedule in Table 6, and VLU Study subjects will also follow the assessment schedule in Table 7, until healing per the CIP definition has occurred. Study-specific assessments may not occur until the ICF has been obtained, and only trained/delegated personnel may conduct study specific assessments. Subjects should return to the study site for their study visits; other local hospitals or clinics should not be used as an alternative.

Some study follow-up visits are not routine care. Routine care post-procedure differs from site to site. However, follow-up visits that are not routine care are not considered burdensome and/or invasive.

VENASEAL SPECTRUM Clinical Investigation Plan

MDT18034

Version 5.0

Page 52 of 164

Medtronic

Table 6: Schedule of Assessments – All Subjects

Data Collection Requirement	Screening	Baseline (<30 days before procedure)	Index Procedure (Day 0)	Day 7 (± 2 days)	Day 30 (± 7 days)	3+ Months Adjunctive Therapy (Optional)	6 Months (± 4 weeks)	12 Months ¹ (± 8 weeks)	24, 36, 48 and 60 Months (± 8 weeks)	Unscheduled ²
Informed Consent	X									
CEAP Clinical Classification (2004 and 2020)	X					X	X	X	X	
Randomization	X									
Demographics, Medical History		X								
Concomitant Medications		X	X							
rVCSS	X			X	X		X	X	X	X
Patient-Reported Symptoms		X		X	X		X	X		
EQ-5D-5L QoL		X			X		X	X	X	
AVVQ QoL	X				X		X	X	X	
SF-36 QoL	X				X		X	X		
VenousTSQ ³					X		X	X		
Duplex Ultrasound		X ⁴	X	X	X		X	X	X	X
Procedure-related Data & Outcome			X							
Physician Satisfaction with Procedure			X							
Patient-Reported Outcomes				X	X		X	X	X	
Reintervention Review				X	X		X	X	X	
Healthcare utilization				X	X		X	X	X	
Adjunctive Therapy Assessment						X	X	X	X	
Adverse Event Assessment			X	X	X	X	X	X	X	X
Device Deficiency Assessment			X							

¹ Subjects in VenaSeal vs. Surgical Stripping Study will be followed through 12 months only.

Medtronic Business Restricted

CONFIDENTIAL

056-F275, v B Clinical Investigation Plan Template

²AE assessments at unscheduled visits are required. Additional assessments are per investigator's discretion; see section 10.11 for additional detail

³VenousTSQe captured at 30 Days; VenousTSQs captured at 30 Days, 6 Months and 12 Months

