- Pain score will be collected during the index procedure and at 7 days and 30 days.
- Return to work and return to normal activities will be assessed at follow-up visits until the subject has returned to each.
- The VenousDQoL consists of two stand-alone questions at baseline, 7 and 30 days, 6, 12, 24, 36, 48 and 60 months (data will be collected through 12 months for subjects enrolled in VenaSeal vs. Surgical Stripping Study).

Questionnaire completion by delegated site personnel

The required study questionnaires such as EQ-5D-5L, VenousTSQ, patient reported symptoms, etc. should be completed in a consistent manner throughout the study. Selecting to complete the required questionnaire on behalf of the subjects should only be if the subjects require it (e.g., vision or literacy issues) and not simply by site or patient preference. The site personnel completing the questionnaire

Medtronic Business Restricted

CONFIDENTIAL

056-F275, v B Clinical Investigation Plan Template

cannot be the treating physician or the PI in order to avoid any bias. If site personnel are assigned to complete the questionnaire on behalf of the subject for one visit, then site personnel should complete for all the remaining visits. Site personnel have to read the complete questionnaire including all the response options. Ideally, the same person will complete the questionnaire with the same subject each time, if at all possible. The questionnaires completed by site personnel may differ from subject questionnaires and may require IRB/EC approval. If necessary, due to COVID-19 restrictions, these questionnaires could also be completed and signed by the subject within 24 hours prior to the follow-up visit. If captured in this manner, care must be taken to ensure the questionnaires are completed and returned to the site prior to the completion of the rest of the visit.

Healthcare Utilization

This study will collect healthcare utilization data related to subject's VRD and care related to the VenaSeal™ closure system to demonstrate total costs over the follow-up period. Specifically, this study will collect:

- Number and type of adjunctive treatments (phlebectomy and sclerotherapy) conducted through 60 months post-index procedure.

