5. EQ-5D-5L
6. AVVQ
7. SF-36 (up to 12-month visit)
8. Patient reported outcomes:
 - a. VenousDQoL
 - b. Patient-reported symptoms (up to 12-month visit)
9. Adjunctive therapy assessment
10. AE assessment
11. Healthcare utilization since last study visit
12. VLU Study:
 - a. Active ulcers: ulcer assessment, ongoing wound care, photographs for core laboratory, healing status
 - b. Post-healing confirmation: recurrence status.

48, 60 months (+/-8 weeks)

Subjects will return to the site for follow-up to conduct the following assessments (limb-specific assessments are of the target limb only). Subjects may also complete 48 and 60 months visit remotely per physician's discretion if subjects cannot return to the site for follow-up.

1. DUS:
 - a. Areas of patency, if any
 - b. Reflux along treatment area
 - c. Evidence of thrombus
2. CEAP classification
3. rVCSS

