
very satisfied 6 5 4 3 2 1 0 very dissatisfied

2. How well do you feel your vein problems are controlled now?

very well controlled 6 5 4 3 2 1 0 very badly controlled

3a. In recent weeks, have you experienced any discomfort or pain related to your treatment?

- no If no, please go straight to Q. 4a.
yes If yes, please answer Q. 3b below.

3b. How bothered are you by the discomfort or pain?

not at all bothered 6 5 4 3 2 1 0 very bothered

4a. In recent weeks, have you experienced any side effects or after-effects of your treatment?

- no If no, please go straight to Q. 5a.
yes If yes, please answer Q. 4b below.

4b. How bothered are you by the side effects or after-effects?

not at all bothered 6 5 4 3 2 1 0 very bothered

5a. In recent weeks, have you worn compression stockings or bandages?

- no If no, please go straight to Q. 6.
yes If yes, please answer Q. 5b below.

5b. How bothered have you been by wearing compression stockings / bandages?

not at all bothered 6 5 4 3 2 1 0 very bothered

continued on the next page ...

VenousTSQs continued ...

6. How satisfied are you with your understanding of your vein problems?

very satisfied 6 5 4 3 2 1 0 very dissatisfied

7a. Have you returned to all your usual activities since your varicose vein procedure?

yes no

Whether you answered yes or no, please answer Q. 7b.

7b. How satisfied are you with the time taken to return to your usual activities?

very satisfied 6 5 4 3 2 1 0 very dissatisfied

8. How satisfied have you been in recent weeks with the effects of the treatment on your independence?

very satisfied 6 5 4 3 2 1 0 very dissatisfied

9. Would you recommend your treatment to someone else who is being offered this vein treatment?

yes, I would definitely 6 5 4 3 2 1 0 no, I would definitely
recommend not recommend
the treatment the treatment

10. If you needed further vein treatment, how satisfied would you be to have the same treatment?

very satisfied 6 5 4 3 2 1 0 very dissatisfied

11. Are there any other aspects of the treatment for vein problems, causing either satisfaction or dissatisfaction, which have not been covered?

yes no

If yes, please describe below.

Thank you for taking the time to complete this questionnaire.

7. VenousDQoL Overview items

VenousDQoL Overview Items

These questions ask about your quality of life – in other words how good or bad you feel your life is.

Please put an "X" in the box that best indicates your response for each item.

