7.9.1.2.2 Endpoint Definition

Return to work is defined as the time in days patients need following a procedure to return to work. Employment status will be captured for all patients. Only patients who have an active employment status (employed or independent worker, including stay at home parents) will be included in the analysis for return-to-work time. Information will be captured on the category of occupation to be able to distinguish between physical and sedentary work. Patients will be censored at the time of study exit.

The other key secondary endpoint to be assessed is the primary target vein closure rate after index treatment. The primary target vein should be the saphenous vein (GSV, SSV, accessory saphenous veins) which at the investigator's discretion is most likely responsible for the greatest portion of the patient's symptoms or pathology. This vein will be treated first.

For subjects treated with the VenaSeal™ system or ETA, anatomic closure of the primary target vein is defined as Doppler ultrasound (DUS) showing primary target vein closure along the entire treated vein segment with no discrete segments of patency exceeding 5 cm. Any areas with >5 cm patency will be measured, and information will be collected on the location of the patency, length of the patency (cm), diameter of the patency (mm), the presence of flow (Y/N), the presence of reflux (Y/N), and the presence of thrombus (Y/N). For subjects treated with surgical stripping, anatomic closure of the primary target vein is defined as the absence of clinically significant refluxing truncal vein incompetency and no discrete segments of patency exceeding 5 cm in the primary target vein. Any areas with vein remnants will be measured and information will be collected on the location of the remnant, length of the remnant (cm), the presence of flow (Y/N), the presence of reflux (Y/N), and the presence of thrombus (Y/N). Lack of anatomic closure on the date of the index procedure will not be considered relevant to this endpoint, since some treatments may not achieve closure immediately.

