7.9.1.2.4 Analysis Methods

For the return to work endpoint, a Kaplan-Meier survival estimator will be used to estimate the survival functions for both the VenaSeal™ and the control arm (i.e., ETA or Surgical Stripping). Day zero is the date of the index procedure. The censoring time is the time to study exit, the later of either the last contact date or the discontinuation date, or the time point for analysis, whichever comes first. A cumulative incidence figure will be produced to compare the two treatments. A log-rank test will be used to test whether the survival distributions differ between the treatment groups. If a patient is reported to have returned to work, but the date of return is unknown, the return date will be imputed from the date of the follow-up visit. For those who have returned to work, the median, Q1, Q3, minimum, and maximum will summarize the number of days to return to work, as well as the number who have not returned to work in each treatment arm.

The treatment effect for primary target vein closure at 6 months, one of the key secondary endpoints, is the difference in the survival curves at time t for each randomized study. A Kaplan-Meier survival estimator will be used to estimate each curve. Day zero is the date of the index procedure. The censoring time is the time to last study visit (scheduled or unscheduled), the time point for analysis, or time to exit, whichever comes first. The non-inferiority test for treatment (VenaSeal) versus control (ETA or Surgical Stripping) will be performed using the test statistic proposed in da Silva, Logan and Klein (2009)³. The Z test statistic will calculate $S_A(t) - S_C(t) + 0.10$ for the numerator where t is at 6 months and the square root of the sum of the Greenwood's variance estimators for each of $S_A(t)$ and $S_C(t)$ in the denominator.

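### Protocol 10.5 follows return to work and normal activities until the subject has returned, but the 10.10 visit lists stop asking after Day 30, while the SAP keeps non-returners at risk to study exit

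*Protocol*

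**What the plan says.** **Protocol 10.5 (other patient-reported outcomes).** The general rule has no Day 30 cut-off: "Return to work and return to normal activities will be assessed at follow-up visits until the subject has returned to each".

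**Protocol 10.10 (visit lists).** The Day 7 list includes "Ability to return to work/normal activities". The Day 30 list repeats it conditionally: "Ability to return to work/normal activities (only if not returned to work/normal activities by 7-day visit"). The list for 6, 12, 24 and 36 months has two entries under patient-reported outcomes: VenousDQoL and "Patient-reported symptoms (up to 12-month visit"). The lists for 48 and 60 months, on site or remote, give VenousDQoL alone.

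**Protocol Table 6.** A generic row, "Patient-Reported Outcomes", is marked at Day 7, Day 30 and every later scheduled visit, without saying which items it covers.

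**SAP 7.9.1.2.2 and 7.9.1.2.4 (return to work, key secondary).** The endpoint definition says "Patients will be censored at the time of study exit". The analysis section adds a time point for analysis as an alternative limit, whichever comes first, but gives none for this endpoint. If a return is reported without a date, "the return date will be imputed from the date of the follow-up visit". The number not returned is to be reported by arm. SAP 7.9.1.7 item 1 (normal activities) and 7.9.2.6 items 1 and 2 (VLU study) use the same censoring rule.

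**The concern.** Censoring at study exit assumes that a return would have been recorded had it occurred. That holds if the question is put at every visit until the answer is yes, as 10.5 requires. It fails at any site that works from the 10.10 lists, where a subject not back at Day 30 is never asked again but stays in the risk set to 12 or 60 months.

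Return to work is one of two formally tested key secondary endpoints. At stake are the late part of the Kaplan-Meier and cumulative-incidence curves, the count of subjects not returned, and the dating of any late returns. A site also cannot tell whether leaving the question out at 6 months is a deviation, since 10.16 lists required assessments not done as one.

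**Working it through.** **1. The plan's own figures for this endpoint.** These are 11 per arm against ETA and 5 per arm against stripping, for 90% power with a two-sided t test at 0.0167. The inputs (protocol 14.1.2, SAP 6.1.2) are means of 0.2 against 3 and 8 days, with SDs of 1.1, 2 and 3. I used the unequal-variance t test, with noncentrality = difference / √((s₁² + s₂²)/n).

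- ETA: 2.8 / √((1.21 + 4)/11) = 4.07; power 90.1% (86.0% at 10 per arm).
- Stripping: 7.8 / √((1.21 + 9)/5) = 5.46; power 92.1% (73.4% at 4 per arm).

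Both reproduce. They do not bear on this point, which concerns data collection and censoring.

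**2. Where the question is named.**

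| Source | Day 7 | Day 30 | 6 months onward |
|---|---|---|---|
| Protocol 10.5 | yes | if not yet returned | if not yet returned |
| Protocol 10.10 lists | yes | if not back by Day 7 | not named |
| Protocol Table 6 | generic row | generic row | generic row |

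Table 6 does not settle the conflict. VenousDQoL alone would explain its later marks, and pain, which 10.10 puts under the same heading, stops at Day 30.

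VenousTSQs item 7a, given at 30 days, 6 and 12 months, asks "Have you returned to all your usual activities since your varicose vein procedure"? It takes yes or no, records no date and does not ask about work. The SAP does not link it to either return endpoint.

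**3. Follow-up treated as event-free if a site uses 10.10.** The Day 30 window ends at day 37 (Table 8).

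- 12 months: (365 − 37)/365 = 89.9%.
- 60 months: (1,825 − 37)/1,825 = 98.0%.

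These are shares of calendar time, not of missed returns, since most returns come early.

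**4. Effect on the curve and the count.** Suppose everyone returns eventually, a fraction f does so after the Day 30 visit, and nobody is asked again. The cumulative incidence then stays at 1 − f until exit, and f is reported as not returned although the true figure is zero. For assumed f of 2%, 5% and 10%, the curve stays at 98%, 95% and 90%. Censoring at the last visit asked leaves essentially the same height but ends the curve where information ends.

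**5. Effect on the log-rank test.** The statistic changes only at event times. If nobody is asked after Day 30, the two censoring rules differ only in who is at risk for events between days 23 and 37. An illustrative simulation used 400 runs and 100 per arm, with exponential return times of mean 2 and 3 days and the same f in both arms, returning on days 38 to 150. All of these inputs are assumed.

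| f | Mean Z, at risk to exit | Mean Z, censored at Day 30 visit | Mean Z, true times |
|---|---|---|---|
| 2% | 2.317 | 2.317 | 2.289 |
| 5% | 1.812 | 1.812 | 1.790 |
| 10% | 1.352 | 1.352 | 1.266 |

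Rejection rates at 0.0167 were also the same under the two censoring rules, and the largest single-run difference in Z was 0.035.

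**6. If only some sites ask at 6 months.** Subjects at the other sites remain in the late risk sets without being able to have an event, so the late event rate is diluted. A return with no date is placed at the visit, day 154 to 210 (Table 8), even if it happened soon after Day 30. The simulation does not cover this mixed case.

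**7. Who could be affected.** SAP Table 1 has six stripping rows. Two have an upper quartile of 28 days. The others give means of 12.4 and 4.2 days and medians of 11.7 and 4.3. The two VenaSeal rows show a mean of 0.2 days and a median of 1 (range 1 to 16). The ETA upper quartiles for return to work are all 14 days or less, although one laser row has a range to 46 days.

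**The case against.** The strongest reply is that 10.5 is explicit and governs. On that reading a return on day 60 is captured at 6 months with its actual date, the visit date being used only when that date is unknown. The 10.10 lists are then merely incomplete, and Table 6 is consistent with 10.5. This stands as a reading of the plan's intent. It does not tell a site working from 10.10 to ask, and neither Table 6 nor item 7a resolves the conflict.

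A reader might infer that the plan asks only at these two visits and counts everyone not back by Day 30 as never returning. The documents do not support that. 10.5 says otherwise, and the SAP censors non-returners rather than coding them as permanent failures.

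A reader might also infer that the tested contrast with stripping is exaggerated. If nobody asks after Day 30, the log-rank result is practically unchanged. If asking varies by site, randomization stratified by site means both arms at a site share its practice, so no arm-specific ascertainment follows directly.

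Finally, a quarter of the stripping arm is a ceiling, not an estimate. It rests on two of six rows, and the Day 30 window runs past day 28. The plan's own assumption (mean 8, SD 3) puts day 30 at (30 − 8)/3 = 7.3 SDs above the mean. These limits are accepted.

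**Conclusion.** The contradiction between 10.5 and 10.10 is real, and the SAP's censoring rule is valid only if 10.5 is followed at every later visit. Where 10.10 is followed, the curves plateau artificially and the number not returned can be overstated. This falls mainly on slow recoverers, most plausibly in the stripping arm.

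The size cannot be fixed from the documents because the case report form is not among them. As a ceiling, a quarter of roughly 108/2 = 54 stripping subjects is 13.5, before restriction to those in active employment; the other rows in SAP Table 1 suggest far fewer. In the ETA study the likely effect is smaller.

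Confidence is high in the contradiction and moderate in its effect on the data. The point should be corrected because it concerns reporting of a tested key secondary endpoint and the remedy is cheap. It is not a finding that the test is biased.

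**What to change.** **Protocol.** Reconcile 10.5 and 10.10 by adding ability to return to work and normal activities, with the date, if not yet returned, to the 6-month and later lists, including the remote-visit list. Make sure the case report form carries the same item.

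**SAP.** In 7.9.1.2.2, 7.9.1.2.4, 7.9.1.7 item 1 and 7.9.2.6 items 1 and 2, censor non-returners at the last visit at which the question was actually asked. Either specify the analysis time point for these endpoints or remove the reference to it. Report the share returned by Day 30 alongside the later non-returner count, not instead of it, so that late returns collected under 10.5 are not set aside.

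**Cost.** One line in the later visit lists and a short, consistent change in the SAP. The downside is that curves end earlier for subjects not asked after Day 30, which reflects what is known about them.
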